9.7.8. Month 6 Procedures

- Perform a physical examination.
- Perform assessments for calculation of Child-Pugh Score.
- Review progression to cirrhosis algorithm.
- Assess and record vital signs (weight, temperature, sitting heart rate, respiratory rate, and sitting blood pressure).
- Subject questionnaires (see [Section 12.2.5](#))
- Perform TE at all study sites with access to the Fibroscan® TE device.
- Perform an ultrasound for HCC surveillance (if equipment is unavailable, sites should make every attempt to use available community referral sites).
- Assess and record AEs.
- Review and record prior and concomitant medications.
- Review and record any nonstudy related medical or surgical treatment procedures and any medically relevant HCP or non-HCP related office visits that have occurred since the previous study visit.
- Assess investigational product compliance, perform investigational product accountability, and review dosing diary with the subject.
- Assess for dose titration, if eligible (refer to [Section 7.4](#)).
- Assess the subject's supply of investigational product to ensure an adequate amount. Access the IWRS and dispense investigational product if necessary.
- Verify that the subject has fasted for at least 8 hours.
 - Record fasting status in the source and CRF.
 - If the subject reports having eaten within 8 hours, document accordingly in the source and CRF and remind the subject that fasting is required prior to all study visits.
- Obtain blood samples for serum chemistry, hematology, and coagulation tests.
- Obtain blood samples for:
 - OCA, C4, and FGF-19
 - Markers of hepatic fibrosis and/or inflammation (including ELF)
- Provide the subject with a dosing diary to document his or her dosing.

- Schedule the next visit, reiterate dosing instructions, and advise the subject:
 - NOT to take investigational product on the morning of the next visit, and
 - To bring the investigational product bottle(s); s/he will dose at the clinic (if this is in compliance with the established dosing frequency), and
 - To fast overnight (at least 8 hours) prior to the next visit. Fasting is required prior to all study visits, but water is permitted.
- For subjects who will participate in the PK assessment and are taking BAS or aluminum hydroxide- or smectite-containing antacids, they should be instructed to not take their regular dose on the morning of the study visit.

9.7.9. Month 9 Procedures

- Perform assessments for calculation of Child-Pugh Score.
- Review progression to cirrhosis algorithm.
- Assess and record vital signs (weight, temperature, sitting heart rate, respiratory rate, and sitting blood pressure).
- Assess and record AEs.
- Review and record prior and concomitant medications.
- Review and record any nonstudy related medical or surgical treatment procedures and any medically relevant HCP or non-HCP related office visits that have occurred since the previous study visit.
- Assess investigational product compliance, perform investigational product accountability, and review dosing diary with the subject.
- Assess for dose titration, if eligible (refer to [Section 7.4](#)).
- Assess the subject's supply of investigational product to ensure an adequate amount. Access the IWRS and dispense investigational product if necessary.
- Verify that the subject has fasted for at least 8 hours.
 - Record fasting status in the source and CRF.
 - If the subject reports having eaten within 8 hours, document accordingly in the source and CRF and remind the subject that fasting is required prior to all study visits, but water is permitted.
- Obtain blood samples for serum chemistry, hematology, and coagulation tests.
- PK assessment in participating subjects at select study sites (see [Section 9.7.10](#)).
- Provide the subject with a dosing diary to document his or her dosing.
- Schedule the next visit, reiterate dosing instructions, and advise the subject:
 - NOT to take investigational product on the morning of the next visit, and

- To bring the investigational product bottle(s); s/he will dose at the clinic (if this is in compliance with the established dosing frequency), and
- To fast overnight (at least 8 hours) prior to the next visit. Fasting is required prior to all study visits, but water is permitted.

9.7.10. Month 9 Procedures for Subjects Participating in Pharmacokinetic Assessment

At selected investigational sites, subjects will have the option to consent to participate in an additional OCA PK assessment. PK samples will be used to support further analysis of OCA exposure-response in subjects with PBC. This is optional and subjects may decline to participate without affecting their involvement in the rest of the study. Consent to participate in the assessment can be given at any point during study participation prior to the Month 9 visit.

Subjects who are following the Child-Pugh B and Child-Pugh C modified dosing regimen may participate in the PK assessment and will dose in the clinic at this visit even if the previous dose was taken less than 3 days prior; however, every attempt should be made to schedule the Month 9 PK visit according to the subject's established dosing schedule.

Following collection of the Month 9 fasted samples (refer to [Section 9.7.9](#), subjects who are participating in the PK assessment will each receive a single dose of investigational product (blinded OCA or placebo tablet) with approximately 240 mL of water. Subjects taking BAS or aluminum hydroxide- or smectite-containing antacids should be instructed to stagger their dosing of investigative product and UDCA, ensuring at least 4 hours between doses of the BAS and/or these antacids and the investigative product (and UDCA).

Serial blood samples will be obtained for measurement of OCA and its conjugates prior to dosing and at 0.5, 0.75, 1, 1.5, 2, 2.5, 3, 4, 5, and 6 hours post dose. Samples should be collected within a window of ± 5 minutes of the scheduled sample time. Subjects should not drink additional water for 1 hour after taking the dose of investigational product and will remain fasted until the 4-hour sample is collected. Lunch will be provided following collection of the 4 hour PK sample; the lunch will be a meal replacement drink with no other food allowed until after the final 6-hour post-dose sample is collected. Samples will be stored for up to 5 years after the end of the study and will be destroyed after 5 years if not analyzed.

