5.5.2. Rationale for Dose

5.5.2.1. Rationale for OCA Dose

The safety and tolerability of multiple doses of OCA have been established in subjects with PBC at doses up to 50 mg. As demonstrated in the Phase 2 PBC studies (Studies 747-201 and 747-202), OCA significantly reduced serum ALP levels at doses of 10 mg, 25 mg, and 50 mg, but with an increase in the incidence and severity of pruritus at higher dose levels. The Phase 3 PBC study (Study 747-301) subsequently evaluated the safety and efficacy of OCA at lower doses of 5 mg (titrated to 10 mg after 6 months based on efficacy and tolerability in the double-blind phase and after 3 months in the open-label phase) and 10 mg; both treatment groups exhibited clinically meaningful improvements in liver biochemistry and were safe and generally well tolerated. Study 747-301 demonstrated that titration of OCA from a starting dose of 5 mg to 10 mg improved tolerance to pruritus relative to 10 mg (56% versus 69% of subjects who experienced pruritus) and minimized dropouts due to pruritus. Based on these data, the approved dosing regimens for OCA for the treatment of patients with PBC are 5 mg and 10 mg.

The majority of efficacy results with OCA, in terms of change in alkaline phosphatase, was observed by 3 months and the time to treatment-emergent pruritus was typically 1 month or less in Study 747-301. Study 747-302 will evaluate the effect of OCA on clinical outcomes using the 5 mg OCA dose for at least 3 months, increasing to 10 mg OCA, if tolerated.

5.5.2.2. Rationale for Modified OCA Doses in Patients Classified with Child-Pugh B or Child-Pugh C Hepatic Impairment

Simulations using a physiologic PK model predicted changes in systemic and liver OCA concentrations associated with changes in the severity of hepatic impairment (Child-Pugh Score). Model simulations predicted that for mild (Child-Pugh A), moderate (Child-Pugh B), and severe (Child-Pugh C) hepatic impairment, total OCA plasma concentrations increase 1.4-, 8.0-, and 13-fold relative to subjects with normal hepatic function, whereas total OCA liver concentrations increase 1.1-, 1.5-, and 1.7-fold, respectively.

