7.3. Planned Dosing Regimen

Subjects will be randomized to treatment with either OCA or matching placebo in a 1:1 ratio. Subjects will be dosed according to their cirrhosis status (as defined [Section 7.5.4](#)) and applicable Child-Pugh Score (see [Section 7.5.5](#)) as outlined in [Section 7.4](#).

Table 3: Planned Dosing Regimen by Cirrhosis and Child Pugh Score

	Scheduled Dosing Regimen	
	Standard	Modified
	Noncirrhotic/ Child-Pugh A	Child-Pugh B or Child-Pugh C
Starting Dose^a (Day 0)	5 mg daily	5 mg once weekly
Titration 1^b (≥Month 3)	10 mg daily	5 mg twice weekly ^c
Titration 2^b (≥6 weeks after Titration 1)	NA	10 mg twice weekly ^c

^a Starting dose based on subject's cirrhosis status and Child-Pugh score at Screening.

^b Planned titration regimen is shown; however, the titration of dose and/or frequency is dependent on subject tolerability, biochemical response, and/or changes in cirrhosis status or Child-Pugh score at any time during the study (see [Section 7.4](#)).

^c Dosing per the twice weekly schedule must be at least 3 days apart.

Non-Cirrhotic or Child-Pugh A

Subjects who are noncirrhotic or classified as Child-Pugh A at screening will receive 5 mg OCA or matching placebo once daily for 3 months. Subjects should titrate to a maximum dose of 10 mg OCA once daily (or matching placebo) at the Month 3 visit or at any study visit following the Month 3 visit based on tolerability of the product and assessment of biochemical response. Up-titration should be considered when ALP and/or total bilirubin are >ULN. A review of safety laboratory results (eg, chemistry, hematology, and coagulation) obtained no more than 2 months prior to the planned up-titration visit must be completed as part of the investigational product tolerability assessment before up-titration can occur (see [Section 7.4.1](#)).

For those subjects that up-titrate to 10 mg, dose may be decreased to 5 mg at any time during the study as considered clinically appropriate (eg, tolerability). Subjects may be titrated back up to a maximum dose of 10 mg once daily based on tolerability and clinical judgment of the Investigator. A review of safety laboratory results obtained within 2 months of the planned up-titration visit date is not required prior to re-challenging a subject up to 10 mg once daily dosing, as long as the decrease in dose/dosing frequency was less than 3 months in duration.

Cirrhotic and Child-Pugh B or C

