Subjects with cirrhosis (see [Section 7.5.4](#)) and classified as Child-Pugh Class B or Child-Pugh Class C will follow a modified dosing regimen, initiating 5 mg OCA or matching placebo once weekly. After a minimum of 3 months dosing once weekly with 5 mg OCA or matching placebo, and following review of the pre-titration laboratory results to assess safety and tolerability, the dosing frequency of 5 mg OCA or matching placebo should be increased to twice weekly (at least 3 days apart). Subjects who have maintained the twice weekly dosing frequency for a minimum of at least 6 weeks, and meet the dose titration criteria should up-titrate to the maximum allowed dose of 10 mg OCA or matching placebo twice weekly.

Investigators may decrease the dosing frequency (back to once weekly) or dose for any subject at any time during the study, as considered clinically appropriate (eg, tolerability).

The dosing regimen should be determined as described shown in [Table 13 Appendix A](#).

Investigators should follow the dosing/titration schedule as shown described in [Section 7.4](#) and [Appendix A](#).

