7.4. Dose Titration Criteria

Dose titration may follow the scheduled dosing regimens described in [Section 7.3](#) or occur due to tolerability concerns or as a result of changes in a subject's cirrhosis status (using histology or non-histological methods as defined in [Section 7.5.4](#) and [Section 7.5.5](#)) or Child-Pugh Score.

Dose titrations may involve increases or decreases in dosing frequency or dose and are dependent on tolerability (as assessed by a review of AEs and safety laboratory results) as well as biochemical response (as assessed by reductions in ALP and/or total bilirubin). In general, down-titration will be done in response to tolerability concerns and can occur at any time while on-study. Up-titration will be done per protocol when subjects have no tolerability concerns and have not achieved an adequate reduction in ALP and/or total bilirubin to within normal limits, or as assessed by the Investigator, or following resolution of a tolerability concern that previously led to down-titration. Up-titrations may only occur to the maximum dose and frequency for each dosing regimen as defined in [Section 7.3](#). A 1-Month and 2 Month Post-Titration Assessment must be performed any time a subject's dose or frequency is up-titrated (see [Section 7.1.2](#) and [Section 9.7.7](#)).

Scheduled Dose Titration - The first dose titration for any subject may occur no earlier than 3 months following initiation of OCA or matching placebo. Subsequent titrations in dose or dosing frequency for subjects following the Modified Dosing Regimens may occur no earlier than 6 weeks (via an unscheduled visit or regular visit- see [Appendix A](#)) following an up-titration.

Tolerability Dose Titration - Investigators may decrease the dosing frequency or dose for any subject at any time during the study, as considered clinically appropriate (eg, tolerability; see Section 7.4.1).

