9.7. Visit Procedures

9.7.1. Visit Windows

Visits should be based on Day 0 (not on the prior visit), eg, Month 3 should ideally occur 3 calendar months (± 2 weeks) following Day 0.

The visit windows are as follows:

Visit or Procedure	Visit Window and/or Interval
Screening	Screening Visit 1 interval is 3 to 8 weeks prior to Day 0. Screening Visit 2 interval is 1 to 6 weeks prior to Day 0. The visit window for Screening 2 visits allows for the repeat biochemistry tests to be collected at least two weeks after the initial biochemistry sample was collected and will ensure ample time to receive lab results. The overall Screening interval is up to 56 days, but screening procedures should not be performed during the last 7 days of the window. See Section 9.7.3 for scenario specific visit windows that may be applicable at Screening.
Day 0	This is the day of randomization. On-treatment visit scheduling should be calculated from this point going forward. (The first dose of investigational product should be taken the next day, on Day 1.)
Month 1	± 1 week (7 days)
Titration Visit – Standard Dosing Regimen	\geq Month 3
Titration Visit 1 – Modified Dosing Regimen	\geq Month 3
Titration Visit 2 – Modified Dosing Regimen	≥ 6 weeks after Titration Visit 1

Visit or Procedure	Visit Window and/or Interval
Titration Visit 3 – Modified Dosing Regimen (Child-Pugh B ONLY)	≥6 weeks after Titration Visit 2
Post-Titration Visit	1 month and 2 months (±1 week [7 days]) from date of titration
Month 3 to Month 12	±2 weeks (14 days)
Quarterly visits (Months 15 to EOS)	±2 weeks (14 days)
EOT (When subject discontinues investigational product)	As soon as possible upon study discontinuation and as near as possible to last dose taken
EOS (When subject terminates the study)	The final study visit; EOS will occur concurrent with EOT if a subject discontinues investigative product at the time the subject's participation in the study ends (eg, withdrawal of consent or study termination by the Sponsor); EOS will occur after the EOT if the subject discontinues investigative product but continues in the study.

EOS = end of study; EOT = end of treatment

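### Section 9.7.10 lets Child-Pugh B/C subjects dose less than 3 days after the previous dose at the optional Month 9 PK visit; the exception is avoidable and a 3-day floor would replace it

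*Protocol*

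**What the plan says.** Protocol Section 9.7.10 describes an optional PK profile at selected sites at Month 9. For subjects on the Child-Pugh B/C modified regimen it says that they "will dose in the clinic at this visit even if the previous dose was taken less than 3 days prior". The same sentence first choice is to avoid this: "every attempt should be made to schedule the Month 9 PK visit according to" the subject's own dosing schedule.

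Other sections bear on the same dose:

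- **Spacing.** Footnote c of the dosing table in the synopsis, of Table 3 (Section 7.3) and of Table 13 (Appendix A) reads: "Dosing per the twice weekly schedule must be at least 3 days apart". None of the three makes an exception for PK visits. The footnote covers twice-weekly dosing only.
- **Clinic dosing.** At Month 6 (Section 9.7.8) subjects are told that they will dose at the next visit only if this fits their established frequency.
- **Ceiling.** Under Section 7.3, subjects on the modified regimen "should up-titrate to the maximum allowed dose of 10 mg OCA or matching placebo twice weekly". Section 7.4 adds: "Up-titrations may only occur to the maximum dose and frequency for each dosing regimen".
- **Window.** Section 9.7.1 allows Month 3 to Month 12 visits to fall within 14 days either side of the target date.

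**The concern.** The 3-day interval is the protocol's own dosing safeguard for hepatically impaired subjects, and Section 9.7.10 waives it for an optional visit with no therapeutic purpose. Section 5.5.2.2 explains why dosing is restricted in this group. For Child-Pugh A, B and C respectively, the sponsor's model predicts that "total OCA plasma concentrations increase 1.4-, 8.0-, and 13-fold relative to subjects with normal hepatic function". The predicted liver concentrations are 1.1-, 1.5- and 1.7-fold.

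Two further matters follow. A profile taken 1 or 2 days after a dose is less comparable with one taken on a due day. Because Section 9.7.10 authorises the short interval, such a profile is arguably not a deviation and would stay in the PK Population of Section 13.1.1. Section 9.7.10 is also silent on what happens to the next scheduled dose, so sites must work that out from other sections.

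**Working it through.** The plan gives no figure to reproduce here. The check is a calendar count.

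**Inputs.** Month 9 window ±14 days (Section 9.7.1), so 14 + 1 + 14 = 29 calendar days. Twice-weekly doses at least 3 days apart (Table 3). A fixed weekly pattern that meets this must be spaced 3 and 4 days, since 3 + 4 = 7. Dosing weekdays are assumed fixed.

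**1. What the exception permits on a twice-weekly schedule.** Put doses on days 0 and 3 of each 7-day cycle.

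| Visit on day | Days since last dose | Days to next scheduled dose |
|---|---|---|
| 0 (due) | 4 | – |
| 1 | 1 | 2 |
| 2 | 2 | 1 |
| 3 (due) | 3 | – |
| 4 | 1 | 3 |
| 5 | 2 | 2 |
| 6 | 3 | 1 |

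The exception applies on days 1, 2, 4 and 5. One interval shrinks from at least 3 days to 1 or 2. Two doses then fall within 3 consecutive days instead of one: 10 mg instead of 5 mg at 5 mg twice weekly, or 20 mg instead of 10 mg at 10 mg twice weekly.

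**2. The following dose.** From days 1, 2, 4 and 5 the next scheduled dose is 2, 1, 3 and 2 days away. In three of the four cases the spacing rule bars keeping it. In the fourth (day 4), keeping it would add a dose beyond twice weekly, which the ceiling in Sections 7.3 and 7.4 bars. If the clinic dose replaces the next scheduled one, the two-week total stays at four doses.

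**3. Room in the window without the exception.** Twenty-nine days are 4 weeks plus 1 day. The ranges below cover every position of the window against the week and every choice of dosing weekdays.

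| | Twice weekly | Once weekly |
|---|---|---|
| Due days, all days | 8–9 | 4–5 |
| Due days, Monday–Friday | 4–5 or 8–9, by weekday pair | 4–5, or 0 if the dose day is Saturday or Sunday |
| Days ≥3 days after last dose, all days | 12–13 (3 per week: 4 × 3 = 12) | 20–21 (5 per week: 4 × 5 = 20) |
| Same, Monday–Friday, worst schedule | 4–5 | 12–13 |

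The worst twice-weekly case is Sunday/Wednesday dosing. Its eligible days are Sunday, Wednesday and Saturday, so only Wednesday is a weekday, giving 4 × 1 = 4. The worst once-weekly schedules (dose day Sunday, Monday, Tuesday or Wednesday) leave three eligible weekdays per week, giving 4 × 3 = 12.

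**4. Does a 3-day floor work off schedule?** The only eligible twice-weekly day that is not a due day is day 6. A clinic dose there replaces the dose due on day 7, and the next follows on day 10, 4 days later. The spacing rule holds throughout.

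**The case against.** The strongest reply is that this is an intended, narrow rule. A specific provision normally governs a general one, and the footnotes need not repeat a carve-out that is stated where it applies. The change summary in Appendix F gives the purpose of the sentence: to make clear that hepatically impaired subjects may take part in the PK assessment. Sites must already try for an on-schedule visit. All of this stands. A reader might infer a drafting slip or an unresolved contradiction, but the text does not support that.

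A second reply concerns feasibility. The visit needs a fasted subject, a pre-dose sample and ten post-dose samples over 6 hours, each within 5 minutes of its time, so staffing may limit the choice of days. A once-weekly subject who doses at the weekend has no due day on a weekday. This also stands. It rules out calling the exception plainly needless on the strength of the due-day counts, and it rules out a rule that the visit must fall on a due day. It does not defeat a 3-day floor, because every schedule keeps eligible weekdays.

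Third, Section 5.5.2.2 reports no apparent effect on the overall safety profile in Child-Pugh B/C subjects in Phase 1 and 2 studies, despite plasma exposures more than 10-fold those of healthy subjects. It also names the liver as the primary site of action. That is a fair counterweight to the 8.0- and 13-fold plasma figures.

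Fourth, the pre-dose sample and the dosing diary make carry-over visible. They do not make a short-interval profile comparable with a due-day one, but the size of the difference cannot be derived from the protocol.

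**Conclusion.** The point holds as a minor one. Section 9.7.10 deliberately waives the protocol's 3-day minimum in Child-Pugh B/C subjects, and the calendar never forces it to: at least 4 eligible weekdays remain in the window for twice-weekly dosing and at least 12 for once-weekly. For once-weekly subjects the conflict is with the Month 6 clinic-dosing instruction, not with footnote c.

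Two stronger readings are not supported. A reader might infer that the exception adds a dose to the week's schedule. The spacing rule and the twice-weekly ceiling prevent that, although Section 9.7.10 does not say so itself. A reader might also infer demonstrated harm from the post-marketing cases in Section 5.7. Those concern dosing at up to 7 times the recommended once-weekly starting dose, the sponsor judged the evidence of causality insufficient, and they do not address one early dose.

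The reach is small: consenting Child-Pugh B/C subjects at selected sites whose visit falls off schedule, about half of them on placebo under 1:1 randomisation. The primary and key secondary analyses are unaffected. The counts assume fixed dosing weekdays and an inclusive window. Site availability is not described and could narrow the choice of days.

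**What to change.** In Section 9.7.10, replace the permission to dose under 3 days with three statements:

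1. The PK visit takes place at least 3 days after the previous dose, within the existing ±2-week Month 9 window.
2. A due-dose day is preferred but not required, so that once-weekly weekend dosers are not shut out at weekday clinics.
3. The clinic dose replaces the nearest scheduled dose still to be taken, and later doses are kept at least 3 days apart.

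The cost is a short rewording of one passage, with no new visit, sample or subject. The downside is slightly less scheduling freedom and an occasional profile not taken when no suitable day can be arranged.
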